#### **2.1.4.1 Adverse events variables**

##### ***Adverse event observation period***

- Pre-treatment adverse events are AEs that developed or worsened or became serious during the pre-treatment period
- Treatment-emergent adverse events are AEs that developed or worsened or became serious during the TEAE period
- Post-treatment adverse events are AEs that developed or worsened or became serious during the post-treatment period

All adverse events (including SAEs and AESIs) will be coded to a lower-level term (LLT), preferred term (PT), high-level term (HLT), high-level group term (HLGT), and associated primary system organ class (SOC) using the version of Medical Dictionary for Regulatory Activities (MedDRA) currently in effect at Sanofi at the time of database lock.

Record the occurrence of AEs (including SAEs and AESIs) from the time of signed informed consent until the end of the study.

**Adverse events of special interest (AESIs)** include the following terms (their complete descriptions are provided in the protocol):

- Pregnancy of a female subject entered in a study as well as pregnancy occurring in a female partner of a male subject entered in a study with IMP selected using the e-CRF “Pregnancy” tick box on the AE page.
- Symptomatic overdose (serious or non-serious) with IMP, selected using the e-CRF “Symptomatic overdose of the IP” tick box on the AE.
- Increase in ALT  $\geq 3 \cdot \text{ULN}$  (if baseline ALT  $< \text{ULN}$ ) or  $\geq 2 \cdot \text{baseline value}$  (if baseline ALT  $\geq \text{ULN}$ ), selected using laboratory data.
- 
- Hypersensitivity:
  - Anaphylactic reactions or acute allergic reactions that require immediate treatment, selected using a CMQ coding list.
  - Severe injection site reactions, selected using HLT=“Injection site reaction” and an intensity equal to severe.
- Tuberculosis, selected using a CMQ coding list.
- Initiation of medications for suspected tuberculosis, selected using a WHODD CDG00737 “initiation of medications for suspected tuberculosis”.

- Acute renal failure, selected using a CMQ coding list.

The summary of CMQ coding lists to be used in determining these AESIs is displayed in [Appendix E](#).

#### **2.1.4.2 Deaths**

The deaths observation period are per the observation periods defined above.

- Death on-study: deaths occurring during the on-study observation period
- Death on-treatment: deaths occurring during the TEAE period
- Death post-study: deaths occurring after the end of the study visit

#### **2.1.4.3 Laboratory safety variables**

Clinical laboratory data consists of blood analysis, including hematology, clinical chemistry, and urinalysis. Clinical laboratory values after conversion will be analyzed into standard international units and international units will be used in all listings and tables.

The laboratory parameters will be classified as follows:

- Hematology
  - **Red blood cells and platelets and coagulation:** hemoglobin, hematocrit, red blood cell count (erythrocytes), platelet count, erythrocyte sedimentation rate (ESR)
  - **White blood cells:** white blood cell count with differential (leukocytes, neutrophils, lymphocytes, monocytes, basophils, eosinophils)
  - **Tuberculosis screen:** a Quantiferon®-TB gold evaluation.
- Chemistry
  - **Metabolism:** glucose, total protein, albumin, creatine kinase (CK), high-sensitivity C-reactive protein (hsCRP), Hemoglobin A1C, Cholesterol, Triglycerides
  - **Electrolytes:** sodium, potassium, chloride, calcium, phosphorous, bicarbonate
  - **Renal function:** creatinine, creatinine clearance, blood urea nitrogen, urate
  - **Liver function:** alanine aminotransferase (ALT), aspartate aminotransferase (AST), alkaline phosphatase (ALP), bilirubin
  - **Pregnancy test:** (For women of childbearing potential)  $\beta$ -HCG blood test, urine pregnancy tests.
  - 
- Serology
  - **Hepatitis screen:** hepatitis B surface antigen, hepatitis B surface antibody, hepatitis B core antibody and hepatitis C antibodies

- [REDACTED]
- Cytometry
  - [REDACTED]
  - Urine samples will be collected as follows:
    - **Urinalysis** (by dipstick): pH, specific gravity, protein, glucose, ketones, occult blood, nitrite, leukocyte esterase, urobilinogen and bilirubin. If any parameter on the dipstick is abnormal, a urine sample should be sent to the central laboratory for testing. If positive for proteins, microscopic analysis is performed by central laboratory.

Technical formulas are described in [Section 2.5.1](#).

#### **2.1.4.4 Vital signs variables**

Vital signs include: heart rate (beats per minute), diastolic and systolic blood pressure (mmHg) after 5 minutes of resting in sitting position and body weight (kg) and height (cm). body mass index (BMI) is calculated automatically at each visit on e-CRF page.

In addition to quantitative variables, the following qualitative variables will be displayed at baseline for weight in kilograms (<50, ≥50 and <100, ≥100), body mass index (BMI) in kg/m^2 (<30, ≥30).

Moreover, the values and changes from baseline in SPO2 over time will be displayed from the “Pulse Oximetry - Oxygenotherapy” e-CRF page and “Pulse Oximetry – Ambient air” e-CRF page separately.

#### **2.1.4.5 Electrocardiogram variables**

A standard 12-lead ECG will be performed and evaluate locally.

ECG parameters include heart rate (beats per minute), PR interval (msec), QRS duration (msec), QT interval (msec), ST deviation (mm), T-wave and U-wave morphologies as normal or abnormal. In addition, ECG assessments will be described as normal or abnormal (clinically significant or not) according to the Investigator’s interpretation on the ECG eCRF page. The corrected QTc (according to Bazett and Fridericia) will be derived afterwards.

#### **2.1.5 Pharmacokinetic variables**

All measurements (scheduled or unscheduled) will be assigned to analysis windows defined in [Table 7](#), in order to provide an assessment of the PK parameter at each time point planned to be collected as per protocol.

Samples for PK analysis are planned to be collected at pre-dose (within 2 hours before each dose administration) during Visits 2 (Day 1), 4 (Week 4), 6 (Week 12), 7 (Week 24), 8 (Week 36) and 9/EOT (Week 52). Pharmacokinetics samples during Visit 10 will be collected in the morning. An additional sample should be taken in a subgroup (at least 30 patients by cohort) between 5 and 10 days after last dose (i.e. after Visit 9). The possibility to perform this additional sample will be discussed between Investigator and patient on a case by case basis.

Pharmacokinetic variable is the SAR156597 concentration at each time point using the time windows defined in Table 8. Depending on the timing of the sample versus the previous injection,  $C_{\text{trough}}$ ,  $C_{\text{trough,av}}$ ,  $C_{\text{max}}$  and  $C_{\text{Follow-Up}}$  will be defined as follows:

- $C_{\text{max}}$ : SAR156597 concentration sample taken 5 to 10 days after last injection (week 52);
- $C_{\text{trough}}$ : SAR156597 concentration sample within 2h before each administration (day 1, week 4, week 12, week 24, week 36 and week 52);
- $C_{\text{trough,av,ss}}$ : SAR156597 average trough concentrations (“ $C_{\text{trough,av,ss}}$ ”) will be calculated for each patient as the mean of “ $C_{\text{troughs}}$ ” considered at steady state (ss). The occurrence of steady state will be assessed graphically, by plotting “ $C_{\text{trough}}$ ” throughout the study visits over all patients.
- $C_{\text{Follow-up}}$ : SAR156597 concentration sample taken in week 64, 14 weeks after last injection.

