	
 • Tolerability at the investigational medicinal product (IMP) injection site: 
 - Erythema (diameter and graded severity) - Swelling/induration/edema (diameter and graded severity) - Pain assessment 
Immunogenicity
 
Testing for anti-drug antibodies (ADA)
 
Biomarker quantification
 
 • Blood biomarkers which may predict response to drug, disease progression and provide evidence of drug action will be collected including but not limited to inter-cellular adhesion molecule 1 (ICAM1), TARC, periostin and HE4 • Archived blood samples will be performed for future assay of protein and mRNA biomarkers related to the diagnosis, progression, or therapeutic responsiveness of IPF 
Pharmacokinetics
 
Population PK analysis of plasma SAR156597 concentrations to predict PK parameters at steady state (Cmax, tmax, AUC0-168 &/or AUC0-336) and time to reach steady state.

ASSESSMENT SCHEDULE
	
The study will comprise 10 on-site visits AND 9 phone calls:
 
 • Visits: 
 - V1 screening visit between D -28 and Day -1 - V2 baseline visit at D1 (first dosing) - during the treatment period*: 
 - visit every 2 weeks from V2 to V5 - every 6 weeks from V5 to V6 - every 12 weeks from V6 to V8 - every 16 weeks from V8 to V9 (Week 52; last dosing) - V10 follow-up visit at Week 64 - A time window of ± 2 days will be allowed for each visit • Phone calls: 
 - For safety considerations at Weeks 8, 16, 20, 28, 32, 40, 44, 48 during the treatment period and at Week 58 during the follow-up period. 
*IMP administration being every week.

STATISTICAL CONSIDERATIONS
	
Sample size determination:
 
Based on prior clinical trial experience in IPF patients, it is estimated that the standard deviation (SD) of the absolute change in % predicted FVC at 52 weeks is approximately 12%. For the primary efficacy parameter of absolute change in % predicted FVC, 92 patients per treatment group will yield 80% power to detect a 5 percentage point difference between the treatment groups and placebo. Additional patients will be randomized in each regimen to allow for dropouts; therefore, approximately 100 patients

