
This dual simultaneous binding of IL-4 and IL-13 is unique to SAR156597, although several other monoclonal antibodies that bind individually to IL-13 have been tested in clinical trials at doses as high as 300 mg subcutaneously and 10 mg/kg intravenously (16).

[REDACTED]

[REDACTED] ed natural killer (NK) cell activity at all doses, and injection site cellular infiltrates at all doses.

The no observed adverse effect level (NOAEL) was considered to be 10 mg/kg/week. SAR156597 is in early phase of clinical development. A placebo-controlled first in man study (TDU11325 study) has shown that single subcutaneous (SC) doses ranging from 10 to 300 mg were safe and well tolerated in healthy subjects. After single SC administration of SAR156597 at doses of 10 to 300 mg, peak concentrations of SAR156597 in plasma (C_{max}) occurred, on average, 4 to 7 days after administration. SAR156597 exposure increased with dose but in a less than dose proportional manner. The overall terminal elimination half-life (t_{1/2z}) was about 15 days and was independent of dose over the dose range of 10 to 300 mg. Low titers of ADA were detected and confirmed in post-dose plasmas from 4 of 36 subjects who received SAR156597.

The repeated ascending dose study (TDR11326) was conducted in patients with IPF to evaluate the safety, tolerability, pharmacokinetics and pharmacodynamics of 3 dose levels of SAR156597 (50, 100, and 200 mg) administered SC once a week over a 6-week period (7 administrations) according to a double-blind, randomized, placebo-controlled, sequential design. A total of 24 patients with IPF were randomized (6 in the placebo group and 18 in the SAR156597 groups). SAR156597 was generally safe and well tolerated. The most commonly reported adverse events (AE) were infections with a comparable incidence across treatment groups. No significant emergent ADA reactivity developed as a consequence of treatment with SAR156597. Steady state of SAR156597 was achieved on Day 43 for all doses. The results of pharmacodynamic data showed that SAR156597 reduced, in an apparent dose-dependent manner from 50 to 200 mg once a week, the plasma level of TARC (or CCL17), a protein directly induced by IL-4 and IL-13 receptor activation. Data for other pharmacodynamics i.e; lung function parameters and other biomarkers, were inconclusive probably due to the short duration of treatment and small sample size of the study.

More detailed information is provided in the Investigator's Brochure.

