4.2.2 Design rationale

The 52-week treatment duration is based on published data from clinical trials in IPF and also from IPF natural history data that respectively showed evidence for treatment-induced changes on surrogate endpoints and significant decline in respiratory function characteristic of disease progression over a 12-month period.

The follow-up period of 12 weeks after dosing for adverse events (AEs) and pharmacokinetic (PK) analysis is appropriate taking into account the estimated half-life of about 11 to 15 days for SAR156597 from the TDU11325 and TDR11326 studies.

Dose selection

SAR156597 was safe and well tolerated at single SC doses up to 300 mg in healthy subjects as well as at repeated SC doses up to 200 mg during 6 weeks in patients with IPF, including at the injection site level.

No *in vivo* data from an appropriate animal model of IPF is available to guide the desired pharmacologically active exposure of SAR156597. However, modelling and simulation of the inhibition of Stat6 phosphorylation in monkey suggest that its inhibition will be fully achieved. Additionally, SAR156597 has been shown to reduce in a dose dependent manner (up to 200 mg once a week) the plasma level of TARC, a protein biomarker involved in the IL-4/IL-13 pathway, after 6 weeks of treatment in patients with IPF.

As the desired dose frequency for patient convenience is once every 2 weeks, the weekly dose regimen for the 200 mg dose level will be compared to the every 2 weeks dose regimen for 200 mg.

Finally, modelling and simulations based on the PK data from the multiple dose clinical study (TDR11326) have confirmed that a 200 mg dose administered once every 2 weeks and once a week give an acceptable safety margin in terms of exposure ratio (monkey AUC at NOAEL/human AUC) of ~6 and ~3 respectively.

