The IMP is administered every 7 days +/- 2 days from initial IMP administration. This is permitted per protocol to accommodate special circumstances, eg. laboratory results pending, ongoing AE, patient scheduling difficulty.

If IMP administration is missed or temporarily discontinued, the initial schedule of injections should be resumed. This does not apply to permanent treatment discontinuation.

On days when the patient has a study visit, the IMP will be administered by the Investigator or delegate after clinic procedures and blood collection.

For doses not administered at the study site, the IMP will be administered by qualified site personnel and /or healthcare professionals (e.g. visiting nurse service).

Patients should be monitored by site personnel/visiting nurse for at least 30 minutes after each administration for potential signs and symptoms that may suggest a hypersensitivity reaction.

[For Czech Republic only per local requirement: Patients should be monitored at the study site by site personnel for a minimum of 2 hours after the first administration of IMP and for a minimum of 1 hour after the next 5 administrations for potential signs and symptoms that may suggest a hypersensitivity reaction. For the subsequent IMP administrations, patients should be monitored by site personnel/visiting nurse for at least 30 minutes after each administration.]

For doses not given at study site, a booklet will be provided to the patient to record information related to the injections; this booklet will be completed by the visiting nurse after each injection and will be kept as source data in the patient's study file. Patients will be instructed to bring the booklet back at the subsequent site visit for Investigator's review.

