**Figure 1 - Graphical study design (screening period, double-blind period and follow-up period)**

R\*: randomization  
Sc: subcutaneous  
D: day  
W: week

Approximately 300 patients will be randomized in a ratio 1:1:1 to the following three treatment arms:

- SAR156597 (qw) arm (n = 100): Patients will receive SAR156597 administered subcutaneously in 200 mg doses once every week (qw)
- SAR156597 (q2w) arm (n = 100): Patients will receive SAR156597 administered subcutaneously in 200 mg doses once every 2 weeks (q2w) alternating with placebo subcutaneously once every 2 weeks
- Placebo (qw) arm (n = 100): Patients will receive placebo subcutaneously once every week.

The study population will be stratified at baseline according to a background therapy with pirfenidone or nintedanib (standard of care for IPF in authorized countries).

The study will last up to 68 weeks as follows:

- Up to 4 weeks of screening
- 52 weeks of study treatment (from Day 1 dosing to Week 52 dosing)
- 12 weeks of follow-up

The total duration will be approximately 64 weeks (excluding screening period) per patient.

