**Table 8 - Time windows for PK variables definition**

PK variables	Time
C max	W52 + 5 to 10 days
C trough	-2h (day 1, Weeks 12,24,36,52)
C follow-up	Week 64

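### The SAP's Cmax is one sample taken 5 to 10 days after the last injection; in the weekly arm day 7 is the trough, so the tabulated peak is not a peak

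*SAP*

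**What the plan says.** SAP 2.1.5 defines Cmax as "SAR156597 concentration sample taken 5 to 10 days after last injection (week 52"). SAP Table 8 gives its window as "W52 + 5 to 10 days", the same for every arm. Table 7 places the sample at study days 370 to 375.

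The same SAP section defines Ctrough as "SAR156597 concentration sample within 2h before each administration (day 1, week 4, week 12, week 24, week 36 and week 52"). Protocol 8.1 fixes the interval between injections: "The IMP is administered every 7 days +/- 2 days from initial IMP administration". In the qw arm, then, Ctrough is nominally a sample 7 days after the previous active dose. Treatment covers "52 weeks of study treatment (from Day 1 dosing to Week 52 dosing"), so a dose is given at Week 52 and the optional sample follows it.

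The protocol never calls this sample Cmax. In 9.3.1.1 and in the flow-chart footnote it is an additional sample in a subgroup of at least 30 patients per arm. Steady-state Cmax belongs elsewhere: the synopsis plans "Population PK analysis of plasma SAR156597 concentrations to predict PK parameters at steady state", listing Cmax and tmax, and protocol 9.3.1.4 says the same. SAP 2.4.6 nevertheless tabulates the sample as Cmax, by arm, in one table with the average steady-state trough.

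**The concern.** In the qw arm one concentration at one time after dosing carries two opposite labels: a sample 7 days after a dose is both a Ctrough and an admissible Cmax. The window then runs three days past the trough.

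The window probably follows the protocol's Introduction, where peak concentrations "occurred, on average, 4 to 7 days after administration". That figure comes from single doses in healthy subjects. Under repeated weekly dosing, drug from earlier doses is declining while the newest dose is absorbed, so the combined curve turns down sooner.

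At stake is the descriptive PK table. Someone reading a peak-to-trough ratio from it, or comparing peak exposure between regimens, would be misled. The trial would also report two different quantities under the name Cmax, one here and one from population PK.

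**Working it through.** **Window.** Table 7 has Week 52 at study day 365. 365 + 5 = 370 and 365 + 10 = 375, which reproduces the stated window.

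**Without a model.** At steady state with interval τ, the concentration τ days after any dose equals the concentration just before that dose. For qw, τ = 7, so the day-7 sample equals the pre-dose value whatever the absorption. After day 7, with no further dose, earlier doses are declining and the last dose is at or beyond its average single-dose peak time of 4 to 7 days. Days 8, 9 and 10 are therefore below trough on average. Of the six days in the window, two are above trough, one equals it and three are below.

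**Inputs for size.**
- Half-life: "estimated half-life of about 11 to 15 days for SAR156597" (protocol 4.2.2), run at 11 and 15 days.
- Single-dose tmax: 4, 5.5 and 7 days (protocol 4.1).
- One compartment, first-order absorption and linear superposition: my assumption.

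**Formulas.**
- ke = ln 2 / half-life; ka solves tmax = ln(ka/ke)/(ka − ke).
- At steady state, t days after the last dose: C(t) ∝ e^(−ke·t)/(1 − e^(−ke·τ)) − e^(−ka·t)/(1 − e^(−ka·τ)).
- Steady state is secure by Week 52: 1 − 2^(−364/15) exceeds 0.999.

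**One case in full** (half-life 11, tmax 4, τ = 7). ke = 0.063, ka = 0.644. C(0) = 1.793, C(5) = 2.006, C(7) = 1.793, C(10) = 1.491, and the peak is 2.196 at 2.2 days. Day 5 / trough = 2.006/1.793 = 1.119. Day 10 / trough = 1.491/1.793 = 0.832. Peak / trough = 2.196/1.793 = 1.225.

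**qw, range over all six cases.**

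| Days after Week 52 dose | Sample / trough |
|---|---|
| 5 | 1.06–1.12 |
| 6 | 1.03–1.06 |
| 7 | 1.00 |
| 8 | 0.94–0.97 |
| 9 | 0.89–0.93 |
| 10 | 0.83–0.89 |

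The modelled qw peak falls 2.2 to 2.8 days after the dose and is 1.09 to 1.23 times trough. The labelled Cmax recovers 91–97% of it at day 5 and 68–82% at day 10. If visits were spread evenly over days 5 to 10 (assumed), the mean ratio to trough would be 0.97 to 0.98. In the case above it is (1.119 + 1.060 + 1.000 + 0.942 + 0.885 + 0.832)/6 = 0.97.

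**q2w (τ = 14).** The order of active and placebo injections is not stated.
- Week 52 injection active: the sample is 5 to 10 days after active drug and is 72–100% of the true q2w peak.
- Week 52 injection placebo: the sample is 7 + 5 = 12 to 7 + 10 = 17 days after active drug and is 46–81% of the true peak.

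Dividing qw recovery by q2w recovery, case by case and day by day, gives 0.92 to 0.97 if active and 1.21 to 1.47 if placebo. The direction reverses.

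**The case against.** The strongest defence is that the window matches the documented time to peak of 4 to 7 days. It does for a single dose, but the Week 52 dose follows a year of weekly dosing, so this does not rescue the label.

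Other objections stand, and they limit the point:

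- A reader might infer that the qw table will show a peak at or below the trough. The documents do not support that. Days 5 and 6 are 3 to 12% above trough, so the result depends on when patients attend. The optional subgroup also differs from the PK population behind the average trough. Could is right; will is not.
- A reader might infer that the qw peak is understated more than the q2w peak. That needs an active Week 52 injection in q2w, which the documents do not state. Even then the relative distortion is only 3 to 8%.
- The variable carries little weight. SAP 1.2.2 frames the PK objective as plasma concentrations, and SAP 2.4.8 names the average trough as the exposure measure for biomarker correlation. The extra plots in SAP 2.4.6 are optional and do not name Cmax.
- The ±2-day dosing window scatters individual ratios. Exposure was less than dose-proportional in the single-dose study, so superposition is approximate. The day-7 equality does not depend on linearity, but it does need a regular 7-day interval.

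**Conclusion.** The label is wrong as written. In the qw arm the sample called Cmax is taken around and after the trough time. The day-7 equality needs only steady state and a regular weekly interval. The sizes rest on the one-compartment model and the protocol's half-life and tmax ranges: a true qw peak of 1.09 to 1.23 times trough at about 2 to 3 days, against a reported value of 1.12 down to 0.83 times trough across the window. The tabulated qw peak could therefore be at or below the trough.

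For q2w, the error cannot be sized until the content of the Week 52 injection is known, and the direction of any between-arm bias is unknown. This is a fault in one descriptive PK summary. It does not reach the primary or secondary efficacy analyses, and it does not show that the protocol's sampling time must change.

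**What to change.** In SAP 2.1.5, 2.4.6 and Table 8, rename the variable as the concentration 5 to 10 days after the last injection. Report it with the actual time since the last active injection; for q2w this means using the kit contents to establish whether the Week 52 injection was active or placebo. Report Cmax only from the population PK analysis that the protocol already plans.

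The cost is SAP wording and one derived time variable. No sample is added or moved. The downside is that no observed Cmax column appears in the study tables, and Cmax is available only from the separate population PK report.
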